#### **Male Patients**

A condom is required for all sexually active male participants to prevent them from fathering a child AND to prevent delivery of study treatment via seminal fluid to their partner while taking azacitidine or decitabine or INQOVI (oral decitabine) and for 3 months after stopping these drugs. In addition, male participants should not donate sperm for the time period specified above.

Prior to starting treatment, male participants are advised to seek consultation on sperm storage and female participants of child-bearing potential should seek consultation regarding oocyte cryopreservation.

#### **8.4.4 Additional safety monitoring and considerations**

[figure not shown]
Due to the known risk of TLS with azacitidine treatment, during this study, subjects should be closely monitored (including relevant laboratory tests) for signs and symptoms of TLS. High risk patients may need additional measures like i.v. hydration and hospitalization; events should be managed per local guidelines. Refer to [Section 6.5.1](#) for guidance on minimizing the risk of TLS and procedures to be followed before initiation of a treatment cycle and during the treatment cycle.

[figure not shown]
#### **8.4.5 Graft versus Host Disease**

For transplanted patients during post-treatment follow up, [REDACTED]

[figure not shown]
#### **8.4.6 Appropriateness of Safety Measurements**

The safety assessments selected are standard for this indication/participant population.

## **9 Study discontinuation and completion**

### **9.1 Discontinuation and completion**

#### **9.1.1 Discontinuation of study treatment**

Study treatment is considered discontinued if stopped earlier than the protocol planned duration. Either the participant or the investigator can initiate study treatment discontinuation.

The investigator must discontinue study treatment for a given participant if, he/she believes that continuation would negatively impact the participant's well-being.

Study treatment must be discontinued under the following circumstances:

- Participant/guardian decision
- Pregnancy

- Use of prohibited treatment as per recommendations in the prohibited treatment (see [Section 6.2.2](#))
- Any situation in which study participation might result in a safety risk to the participant
- Any adverse events or laboratory abnormalities that in the judgement of the investigator, taking into consideration the participant's overall status, prevents the participant from continuing participation in the study
- Protocol-defined reasons for discontinuation (see [Section 6.1.4](#))
- Progression of disease (including transformation to acute leukemia per WHO 2016 classification, as defined as  $\geq 20\%$  blasts in bone marrow and/or peripheral blood), unless specific criteria to continue study treatment, in case there is no acute leukemia reported, as per [Section 6.1.4.1](#), are met
- Termination of the study by Novartis
- Participants who are scheduled for hematopoietic stem-cell transplant (HSCT) or chemotherapy at any time during the course of the study
- Transition to commercial supplies

If discontinuation of study treatment occurs, the investigator should make a reasonable effort to understand the primary reason for the participant's premature discontinuation of study treatment and record this information.

Participants who discontinue study treatment or who decide they do not wish to participate in the study further should NOT be considered withdrawn from the study UNLESS they withdraw their consent (see [Section 9.1.2](#)). **Where possible, they should return for the assessments indicated** in the Assessment Schedule. If they fail to return for these assessments for unknown reasons, every effort (e.g. telephone, e-mail, letter) should be made to contact the participant/pre-designated contact as specified in the lost to follow-up section ([Section 9.1.3](#)). This contact should preferably be done according to the study visit schedule.

If the participant cannot or is unwilling to attend any visit(s), the site staff should maintain regular telephone contact with the participant, or with a person pre-designated by the participant. This telephone contact should preferably be done according to the study visit schedule.

For participants who discontinue treatment for reasons other than pregnancy, death, lost to follow-up, or withdrawal of consent, efficacy assessments must continue to be performed every 2 months as per hematology assessment and at least every 6 months as per bone marrow assessment or as clinically indicated until the end of the study, death, lost to follow-up, or withdrawal of consent.

In some circumstances participants may be allowed to continue to receive study treatment beyond disease progression as per criteria described at [Section 6.1.4.1](#). These participants will continue assessments as outlined in the assessments section ([Section 8](#)), and will complete the EOT visit only after permanent discontinuation of study treatment.

### **9.1.2 Withdrawal of informed consent**

Participants may voluntarily withdraw consent to participate in the study for any reason at any time. Withdrawal of consent occurs only when a participant:

- Does not want to participate in the study anymore, and
- Does not allow further collection of personal data

In this situation, the investigator should make a reasonable effort (e.g. telephone, e-mail, letter) to understand the primary reason for the participant's decision to withdraw his/her consent and record this information.

Study treatment must be discontinued and no further assessments conducted, and the data that would have been collected at subsequent visits will be considered missing.

Further attempts to contact the participant are not allowed unless safety findings require communicating or follow-up.

All efforts should be made to complete the assessments prior to study withdrawal. A final evaluation at the time of the participant's study withdrawal should be made as detailed in the assessment table.

Novartis will continue to keep and use collected study information (including any data resulting from the analysis of a participant's samples until the time of withdrawal) according to applicable law.

All biological samples not yet analyzed at the time of withdrawal may still be used for further testing/analysis in accordance with the terms of this protocol and of the informed consent form.

### **9.1.3 Lost to follow-up**

For participants whose status is unclear because they fail to appear for study visits without stating an intention to discontinue or withdraw, the investigator must show "due diligence" by documenting in the source documents steps taken to contact the participant, e.g. dates of telephone calls, registered letters, etc. A participant should not be considered as lost to follow-up until due diligence has been completed or until the end of the study.

### **9.1.4 Early study termination by the sponsor**

The study can be terminated by Novartis at any time for any reason. This may include reasons related to the benefit/ risk assessment of participating in the study, practical reasons (including slow enrollment), or for regulatory or medical reasons. In taking the decision to terminate, Novartis will always consider the participant welfare and safety. Should early termination be necessary, participants must be seen as soon as possible (provide instruction for contacting the participant, when the participant should stop taking drug, when the participant should come for a final visit) and treated as a prematurely withdrawn participant. The investigator may be informed of additional procedures to be followed in order to ensure that adequate consideration is given to the protection of the participant's interests. The investigator or sponsor depending on the local regulation will be responsible for informing IRBs/IECs of the early termination of the trial.

### **9.1.5 Extension phase**

Patients completing core phase of 12 months and requiring continuation of study treatment (by investigator decision) beyond 1 year will enter the extension phase. For patients that will receive treatment in the extension phase, they are allowed to continue treatment with MBG453 and

azacitidine/decitibine/INQOVI (oral decitibine), azacitidine/decitibine/INQOVI (oral decitibine) alone, or MBG453 alone.

Additionally, for participants who discontinue any study treatment for reasons other than documented disease progression, death, lost to follow-up, or withdrawal of consent, will enter the extension phase.

Efficacy assessments (hematology and bone marrow aspirate/biopsy) should follow [Table 8-1](#). Response assessments must continue to be performed every 3 cycles as per hematology assessment and at least every 6 cycles as per bone marrow assessment or as clinically indicated until documented disease progression/relapse (per IWG criteria [Table 8-2](#)), death, lost to follow-up, or withdrawal of consent.

Drug will be supplied as per [section 6.1.4](#) Also patients who will receive HSCT will be included in the extension phase. Patients will be followed up for efficacy and safety as per [Table 8-1](#) up to 24 months post last patient first treatment. Once they complete the extension phase or end treatment due to progression or any reason excluding HSCT, death, lost to follow up, or withdrawal of consent, patients will enter the post-treatment safety follow up. Participants on the extension period can be contacted by telephone every 6 cycles (24 weeks) to follow-up on their survival status.

#### **9.1.6 Post treatment safety follow up period**

Post treatment safety follow up period is for 150 days for safety and until end of study for survival follow up.

All patients on the study should enter the post treatment safety follow up period. Patients can enter the post treatment safety follow up period any time during the study based on discontinuation or completion of prior core phase or extension phase. Reasons for entering the post treatment safety follow up period can be completing the extension phase or ending treatment due to progression. Any new antineoplastic therapies and transfusions that have been started since the previous contact will be collected. HSCT information will also be collected during these phone calls and [REDACTED] will be collected as part of the safety follow up. Participants on the post treatment safety follow up period can be contacted by telephone every 6 cycles (24 weeks) to follow-up on their survival status.

### **9.2 Study completion and post-study treatment**

Study completion (Core) will occur when the last patient completes the 12 month core phase and safety follow-up or discontinues early.

The end of the study (Last Patient Last Visit) is defined as once all patients discontinued study treatment and were transitioned to treatment outside the study and have completed the study which is targeted at the latest 29 months after the last patient was enrolled. The Last Patient Last Visit will include all the required safety follow-up visits.

At the end of the study, every effort will be made, in alignment with local regulations, to continue provision of MBG453 (sabatolimab) outside this study through an alternative setting to participants who are receiving treatment with MBG453 (sabatolimab) and in the opinion of the investigator are still deriving clinical benefit. Options for continued treatment with MBG453

(sabatolimab) may include access to commercially available drug, or managed access program, or a roll-over study

## **10 Safety monitoring and reporting**

### **10.1 Definition of adverse events and reporting requirements**

#### **10.1.1 Adverse events**

An adverse event (AE) is any untoward medical occurrence (e.g. any unfavorable and unintended sign [including abnormal laboratory findings], symptom or disease) in a participant or clinical investigation participant after providing written informed consent for participation in the study. Therefore, an AE may or may not be temporally or causally associated with the use of a medicinal (investigational) product.

The investigator has the responsibility for managing the safety of individual participant and identifying adverse events.

Novartis qualified medical personnel will be readily available to advise on trial related medical questions or problems.

The occurrence of adverse events must be sought by non-directive questioning of the participant at each visit during the study. Adverse events also may be detected when they are reported by the participant during, between visits or through physical examination findings, laboratory test findings, or other assessments.

Adverse events must be recorded under the signs, symptoms, or diagnosis associated with them, accompanied by the following information (as far as possible) (if the event is serious refer to [Section 10.1.2](#)):

1. The adverse events will be assessed and graded according to the Common Terminology Criteria for Adverse Events (CTCAE) version 5.0,
2. its relationship to the study treatment. If the event is due to lack of efficacy or progression of underlying illness (i.e. progression of the study indication) the assessment of causality will usually be 'Not suspected.' The rationale for this guidance is that the symptoms of a lack of efficacy or progression of underlying illness are not caused by the trial drug, they happen in spite of its administration and/or both lack of efficacy and progression of underlying disease can only be evaluated meaningfully by an analysis of cohorts, not on a single participant,
3. its duration (start and end dates) or if the event is ongoing, an outcome of not recovered/not resolved must be reported,
4. whether it constitutes a SAE (see [Section 10.1.2](#) for definition of SAE) and which seriousness criteria have been met,
5. action taken regarding with study treatment

All adverse events must be treated appropriately. Treatment may include one or more of the following:

- Dose not changed

- Dose Reduced/increased
- Drug interrupted/withdrawn

6. its outcome (i.e. recovery status or whether it was fatal)

If the event worsens the event should be reported a second time in the CRF noting the start date when the event worsens in toxicity.

Once an adverse event is detected, it must be followed until its resolution or until it is judged to be permanent (e.g. Continuing at the end of the study), and assessment must be made at each visit (or more frequently, if necessary) of any changes in severity, the suspected relationship to the interventions required to treat it, and the outcome.

Conditions that were already present at the time of informed consent should be recorded in medical history of the participant.

Adverse events (including lab abnormalities that constitute AEs) should be described using a diagnosis whenever possible, rather than individual underlying signs and symptoms. When a clear diagnosis cannot be identified, each sign or symptom should be reported as a separate adverse event.

Adverse event monitoring should be continued for at least:

- 30 days following the last dose of azacitidine or decitabine or INQOVI (oral decitabine), or 150 days following the last dose of MBG453 (sabatolimab), whichever is later (After the safety follow-up on site visit on Day 30, participants will be followed via telephone call for the Day 90 and Day 150 (or onsite visit if patient happens to be visiting the site)).

OR

- Until the start of a new post treatment antineoplastic medication if sooner than the 150 days mentioned above. If a patient starts post treatment antineoplastic medication, then only adverse events suspected to be related to study treatment should be collected, up to 150 days after discontinuation of MBG453 (sabatolimab).

Adverse events separate from the progression of malignancy (i.e. deep vein thrombosis at the time of progression or hemoptysis concurrent with finding of disease progression) will be reported as per usual guidelines used for such events with proper attribution regarding relatedness to the drug. Information about adverse drug reactions for the investigational drug can be found in the Investigator's Brochure (IB).

Abnormal laboratory values or test results constitute adverse events only if they fulfill at least one of the following criteria:

- they induce clinical signs or symptoms
- they are considered clinically significant
- they require therapy

Clinically significant abnormal laboratory values or test results must be identified through a review of values outside of normal ranges/clinically notable ranges, significant changes from baseline or the previous visit, or values which are considered to be non-typical in participants with the underlying disease.

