### 10.1.3 SAE reporting

To ensure participant safety, every SAE, regardless of causality, occurring after the participant has provided informed consent to 30 days after the date of the last actual administration of HMA

or 150 days after the last dose of MBG453 (sabatolimab), whichever is later and it must be reported to Novartis safety within 24 hours of learning of its occurrence. Any SAEs experienced after the 150 day safety follow-up period should only be reported to Novartis safety database if the investigator suspects a causal relationship to study treatment.

Detailed instructions regarding the submission process and requirements are to be found in the investigator folder provided to each site.

The following SAE reporting timeframes apply:

1. Screen Failures (e.g. a participant who is screened but is not treated or enrolled) SAEs occurring after the participant has provided informed consent until the time the participant is deemed a Screen Failure must be reported to Novartis
2. Treated participants: SAEs collected between the time the participant signs ICF to 30 days after the date of the last actual administration of HMA or 150 days after the last dose of MBG453 (sabatolimab), whichever is later or stopped study treatment

All follow-up information for the SAE including information on complications, progression of the initial SAE and recurrent episodes must be reported as follow-up to the original episode within 24 hours of the investigator receiving the follow-up information. An SAE occurring at a different time interval or otherwise considered completely unrelated to a previously reported one must be reported separately as a new event.

Disease progression (including fatal outcomes) has to be documented as an efficacy assessment and should not be reported as a serious adverse event, except if the investigator considers that the disease progression is related to study treatment.

If the SAE is not previously documented in the Investigator's Brochure or US Package Insert (new occurrence) and is thought to be related to the study treatment, a Novartis Chief Medical Office & Patient Safety (CMO & PS) Department associate may urgently require further information from the investigator for health authority reporting. Novartis may need to issue an Investigator Notification (IN) to inform all investigators involved in any study with the same study treatment that this SAE has been reported.

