2.8 Safety analyses

For all safety analyses, the safety set will be used.

Safety summaries (tables, figures) include only data from the on-treatment period with the exception of baseline data, which will also be summarized where appropriate (e.g. laboratory shift tables). In particular, summary tables for adverse events (AEs) will summarize only on-treatment events, with start date during the on-treatment period (treatment-emergent AEs).

The overall observation period will be divided into three mutually exclusive segments:

- **Pre-treatment period:** from day of subject's informed consent to the day before first administration of study treatment
- **On-treatment period:** from day of first dose of study treatment to last dose of study treatment and up to 30 days after last administration of study treatment.
- **Post-treatment period:** starting at day 31 after last administration of study treatment (MBG453 or HMA).

Overall safety period: from date of first administration of study treatment to 30 days after the date of the last administration of HMA or 150 days after the last dose of MBG453 whichever is later.

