In the AE summaries, the primary system organ class will be presented alphabetically, and the preferred terms will be sorted within primary SOC in descending frequency. The sort order for the preferred term will be based on their frequency in the MBG453 + HMA arm. The summaries will show ‘All grades’ (including AEs with missing grade) and ‘Grades ≥ 3 ’.

The following adverse event summaries will be produced selecting all or a subset of AEs depending on seriousness, relationship to study treatment, outcome or action taken:

- AEs (all AEs by SOC and by PT) and separately those considered related to study treatment and all AEs by HMA
- SAEs and separately those considered related to study treatment
- SAEs with number of occurrences (an occurrence is defined as >1 day between start and prior end date of record of same preferred term).
- Non-SAEs
- SAEs with fatal outcome and separately those considered related to study treatment
- AEs leading to study treatment or MBG453/HMA discontinuation and by HMA
- Related to study treatment AEs leading to study treatment discontinuation
- AEs leading to dose adjustment/interruption for (MBG453/HMA) and study treatment
- AEs requiring additional therapy
- COVID-19 related adverse events by MedDRA COVID-19 (SMQ) terms.

AEs will be summarized by number and percentage of subjects having at least one AE, having at least one AE in each primary system organ class (SOC) and for each preferred term (PT). A subject with multiple occurrences of an AE will be counted only once in the respective AE category. A subject with multiple CTCAE grades for the same preferred term will be summarized under the maximum CTCAE grade recorded for the event. AEs will be assessed according to the Common Terminology Criteria for Adverse Events (CTCAE) version 5.0.

In addition, all AEs and SAE by SOC and PT will be also provided on the overall safety period.

Adverse events for safety follow up period (day 31-150 after last dose of study drug) will be described by system organ class and preferred term.

For the legal requirements of ClinicalTrials.gov, two required tables on <on-treatment/treatment emergent> adverse events which are not serious adverse events with an incidence greater than X% and on <on-treatment/treatment emergent> serious adverse events and SAE suspected to be related to study treatment will be provided by system organ class and preferred term on the safety set population.

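### Late all-causality AE tables run to day 150 with no cut at new antineoplastic therapy, although only suspected-related AEs are collected after it starts

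*Protocol*

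**What the plan says.** **Collection.** Protocol 10.1.1 sets AE monitoring to 30 days after the last HMA dose or 150 days after the last MBG453 dose, whichever is later, with an alternative end point: "Until the start of a new post treatment antineoplastic medication if sooner than the 150 days mentioned above". After that point, "then only adverse events suspected to be related to study treatment should be collected, up to 150 days after discontinuation of MBG453".

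**SAEs.** Protocol 10.1.3 covers "every SAE, regardless of causality, occurring after the participant has provided informed consent", to 30 days after the last HMA dose "or 150 days after the last dose of MBG453 (sabatolimab), whichever is later and it must be reported to Novartis safety within 24 hours". It makes no exception for participants who have started new therapy, and 10.1.1 makes none for serious events. Protocol 6.5.1 requires AE follow-up of all patients over the same window without mentioning the narrowing. The follow-up rows of Table 8-1 do not mention it either, although a footnote refers to 10.1.1.

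**Tabulation.** SAP 2.8 defines an overall safety period that starts at first dose and ends at the same limit as AE monitoring: 30 days for HMA or 150 days for MBG453, the later of the two. SAP 2.8.1 then states: "In addition, all AEs and SAE by SOC and PT will be also provided on the overall safety period". It adds: "Adverse events for safety follow up period (day 31-150 after last dose of study drug) will be described by system organ class and preferred term". AEs after transplantation or antineoplastic therapy are to be listed and flagged; no table is cut, re-denominated or footnoted. SAP 2.1 takes the number of subjects in the relevant population or subgroup as the denominator for percentages, and SAP 2.8 uses the safety set for all safety analyses.

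**The concern.** Within one table, the meaning of having no event changes part-way through follow-up. Before new therapy, an empty record means that no AE was reported. Afterwards it means that no AE suspected to be related was reported. A table headed as all AEs treats the two alike, and a flag in a listing cannot restore events that were never collected.

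The participants affected are not a random subset. Progression, scheduled transplant or scheduled chemotherapy requires treatment to stop (Protocol 9.1.1), and new antineoplastic therapies are recorded during follow-up (Protocol 9.1.6). Collection therefore narrows mainly in participants who have done badly. The 150-day window follows participants well beyond the 30-day on-treatment period, and a reader will take its tables as complete unless told otherwise.

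Serious and non-serious events may also be ascertained differently after the switch, depending on which protocol section a site follows.

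**Working it through.** **The plan's own figure.** The documents contain no calculation on this point. Their only AE-incidence calculation is the sample size, which reproduces: 1.96² × 0.30 × 0.70 / 0.10² = 80.67, so 81. It has no bearing on the argument.

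**Direction.** SAP 2.8.1 counts a participant once per AE category. Uncollected events can remove a participant from the numerator but never add one, while the denominator stays fixed, so any error is downward. It is zero if nobody starts new therapy in the window. It is smaller in the overall-period table than in the day 31-150 table, because some participants will already be counted for the same term from the on-treatment period.

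**Size, as an illustration only.** The documents supply the window (days 31-150, 120 days) and N = 39. Everything else is assumed:
- p: true all-causality incidence over days 31-150, at a constant hazard that is the same in switchers and non-switchers
- f: share of participants starting new therapy (10%, 30%, 50%)
- s: day on which they start (31, 60, 90)
- u: share of their later events judged unrelated and so not collected (50%, 80%, 100%)

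Effective observed fraction of the window for a switcher: e = [(s − 30) + (1 − u)(150 − s)] / 120.

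Tabulated incidence: (1 − f)p + f[1 − (1 − p)^e].

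Worked case with p = 30%, f = 30%, s = 60, u = 80%:
- e = (30 + 0.2 × 90)/120 = 0.40
- 1 − 0.7^0.40 = 0.133
- tabulated = 0.7 × 0.30 + 0.3 × 0.133 = 25.0%, or 39 × 0.050 = 2.0 participants missed

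Ranges over all s and u:

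| f | Tabulated, true 30% | Missed of 39 | Tabulated, true 50% | Missed of 39 |
|---|---|---|---|---|
| 10% | 27.0-29.3% | 0.3-1.2 | 45.1-49.1% | 0.4-1.9 |
| 30% | 21.1-28.0% | 0.8-3.5 | 35.2-47.2% | 1.1-5.8 |
| 50% | 15.1-26.7% | 1.3-5.8 | 25.3-45.3% | 1.8-9.6 |

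**Does a date cut alone help?** Cutting at day s drops every later event in switchers, which is the same as u = 100%. In the worked case e becomes 30/120 = 0.25, and the crude percentage moves from 25.0% to 23.6%. Ascertainment is now uniform, but the understatement is slightly larger. Censoring at day s and estimating cumulative incidence returns 30% in expectation, provided switching is non-informative.

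**SAEs after new therapy, side by side.** An unrelated SAE at that point falls outside collection under 10.1.1 read literally and is mandatory under 10.1.3. If 10.1.3 is applied, SAE counts stay complete and only non-serious unrelated events are lost. If 10.1.1 is applied, unrelated SAEs are lost as well.

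**The case against.** - **The collection rule is a reasonable design choice.** It avoids charging a later drug's toxicity to the study combination, and the trial is single-arm and descriptive. This stands. The difficulty lies with tables that are labelled and denominated as if the rule did not exist.
- **The tables are additional.** A reader might infer that the primary safety results are biased. The documents do not support that: SAP 2.8 limits the main treatment-emergent summaries to 30 days after last dose, so they are affected only if new therapy starts within those 30 days. Nor are these the only summaries of late outcomes, since SAP 2.8.2 summarizes all deaths, including those recorded only on the survival form.
- **The denominator is inferred.** SAP 2.8.1 names none for the day 31-150 table, and table layouts sit in a separate document that is not available here. The inference rests on SAP 2.1 and 2.8, which as written give the safety set.
- **The size is assumed.** This is correct, and the ranges above are not estimates for this trial.
- **The SAE sections differ in scope.** One can read 10.1.1 as the general AE rule and 10.1.3 as the specific SAE rule, which makes outright contradiction too strong a reading. What remains is a mismatch: neither section acknowledges the other's condition, so sites could record different data.
- **It is late.** The latest SAP addendum was issued after database lock, and events not collected cannot be recovered. The way they are tabulated can still be changed.

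**Conclusion.** The concern holds in limited form. Followed as written, the overall-period and day 31-150 tables mix full and related-only collection over a fixed denominator and can only understate all-causality incidence.

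The direction is certain; the size cannot be derived from the documents. Under the assumed inputs, a true 30% would appear as roughly 15% to 29%, or about 0.3 to 5.8 of 39 participants missed, and the loss is nil if nobody starts new therapy in the window. This rests on the safety set being the denominator and on sites following 10.1.1 for non-serious events.

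This is a minor but worthwhile correction to supplementary tables. It does not call the main safety analysis into question.

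**What to change.** In SAP 2.8.1:
1. Cut the all-causality overall-period and day 31-150 tables at the start of new antineoplastic therapy.
2. Present them with time at risk: exposure-adjusted rates, censored cumulative incidence, or at least the number still under full collection. The cut must not be made with N unchanged.
3. Tabulate study-treatment-related AEs separately to day 150.
4. Footnote the collection rule, and label the change as made after database lock.

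Reconcile Protocol 10.1.1 with 10.1.3, 6.5.1 and Table 8-1 on SAEs after new therapy, and state in the report which rule was applied.

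The cost is a little programming. The start date of new therapy should already be to hand, because SAP 2.7.1.2 censors PFS by it and SAP 2.4.2 summarizes these therapies. The drawbacks are fewer events and days in the late all-causality tables and, for the censored estimate, an assumption that switching is non-informative. That assumption is open to doubt when switching follows progression and should be stated beside the result.
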